CRYING, **U**NSETTLED, **D**IS**T**RESSED **I**NFANTS: **E**FFECTIVENESS **S**TUDY

Statistical Analysis Plan

Chief Investigator: [name]

Senior Trial Statistician: [name]

Data Manager and Statistician: [name]

Version and Date V1.4 17.08.22

History of versions

| Version (date) | Changes from prior version | Origin of demand |
|-----------------|--|---|
| V0.1 (09/06/22) | 
Changes from the initial statistical plan included in the study plan:
 
 • Use regression analysis at a daily entry level instead of overall mean crying time. • Primary analysis is to adjust for pre-defined potential effect modifiers. • Even if diaries have missing data, they are to be considered for analysis if at least 7/14 days are filled in. • Specification on assumptions to be tested. • Worse and best-case scenarios to account for missing diaries. | The TSC asked the DMC to consider improving the statistical plan and use an analysis accounting for reported individual daily crying times. |
| V0.2 (24/06/22) | 
 • Improvements in describing datasets • Agreed on co-factors that are to be entered in main regression analysis: baseline crying time, infant age, days within trial and expected outcomes. • Sensitivity analysis added to account for potential performance differences between groups. • Dummy tables added. | Decisions made by the statistical team to improve the plan. |
| V0.3 (07/07/22) | 
 • Improved details on blinding of statistician. • Improved description of primary outcome and way to calculate daily crying time from diaries. • Detailed description of way to test assumptions. | Final plan written by the statistical team for validation by the TMG. |
| V1.0 (17/07/22) | 
 • Improving description of regression analysis. | Validated version by the TMG. |
| V1.2 (28/07/22) | 
 • Improved description for datasets and metadata files. | Statistical team |
| V1.3 (04/08/22) | 
 • Improving description of way to test assumptions. | Statistical team |
| V1.4 (17/08/22) | 
 • Description of how to manage missing data within diaries. • Description of how to impute values for diaries missing crying time in minutes during crying hours. • Sensitivity analysis of results without missing diary imputation. | Validation by TSC. |

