1. Description of study

Background:

Infants who excessively cry, are distressed and unsettled can have a marked impact on family life. Around 1 in 6 families are affected, it is associated with maternal depression, anxiety and loss of parenting confidence. These infant behaviors are usually self-limiting (subsiding around 12 weeks after birth) but during this difficult period many parents look for additional support. There is limited research and therefore much debate about the effectiveness of manual therapy and osteopathic care for these infants.

Aim:

To evaluate the effectiveness and healthcare cost of osteopathic care for excessively crying, unsettled and distressed infants (< 10 weeks old).

[figure not shown]
Study design:

[figure not shown]
A two-arm pragmatic randomised controlled trial to assess the effectiveness of osteopathic manual therapy on infant crying time. We will need to randomize 112 parent(s)/carers and their infants to either: i) Osteopathic manual therapy with best usual care advice and support or, ii) Light non-specific touch attention control (equal time spent with infant) with best usual care advice and support. Parents will be blinded to whether their infant receives the manual therapy care or not. The cost of the delivery of the intervention will be determined and compared with data about the cost of other care.

Population: Healthy infants under 10 weeks old, reported by their parent(s)/carers as excessively crying, unsettled and distressed and difficult to console using the Rome IV criteria (> 3 hours of crying per day, for 3 days for 1 week or more). Infants with diagnosed health conditions for which they are receiving medical treatment, or who would not normally be suitable for osteopathic treatment will be excluded from the study.

Outcomes: The primary outcome is reduced average daily infant crying time over 14 days, collected via parent reported diaries. Secondary outcomes are: i) Parental self-efficacy ii) Parent perceived global improvement iii) Satisfaction and experience with treatment and iv) Adverse events.

Diagram 1. Study scheme flow chart

2. Source documents

Crying diary (participant self-report)

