Statistical blinding will be assured to generate summary variables and set the final analysis for between group differences. Once the final statistical coding is defined and validated by the TSC, the true group identity will be revealed and additional descriptive information on treatment will be provided.

- Coding allocation to random A, B to blind first step of statistical analysis
- Treatment description included in separate dataset to be coded with different IDS than main dataset.

5. Outcome measures

Primary Outcome measure

Crying time diary

The main outcome is daily crying time in minutes. This can be measured for crying times from the first day after treatment to the thirteenth day after treatment. Daily crying time is obtained by adding hourly reported crying times from 6AM to 5:59AM the next day. D-1 is computed from the hourly reported crying time on the day prior to the treatment if the entire day is completed. When incomplete, it is replaced by the parent reported 24h baseline crying time (castor.csv). Daily crying time is considered as missing if any of the time hour slots has missing values within the day.

The primary outcome is the between group average difference in crying time from day 1 after the treatment to day 13 after the treatment. Repeated measures random linear mixed effect adjusting for baseline crying time, expectations for treatment outcome and infant's age is used to estimate the between group difference.

If diaries only report the presence of crying during each hour slot, then each time slot is replaced by the corresponding median reported crying time for infants that were crying during that hour on that specific day of follow-up.

Secondary Outcome measure

Parent Confidence

Changes of parent confidence will be measured using the Parent Confidence Score at baseline and 14 day follow up. This score relies on 15 questions about parenting confidence with a likert scale of 4 choices (0 to 45 points). Changes over time will be measured at an individual level by adding the baseline value as a dependant variable in the mixed effect model. Movement of 6 points or more is to be considered as meaningful.

Global change

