- Analyse potential correlations between missing data in diary and overall summary measures.

Missing data for hourly entries will not be replaced (e.i. not missing total at random) unless parents did not report minutes in an explicit was. Graphical representations are replaced by estimates of hourly crying time. Reported crying within a hourly time slot without specification on the duration is replaced by the median observed crying time from other reported crying for that specific time slot (i.e. hour of the day and day of the trial).

Given the nature of the analysis, missing data within the diary will only reduce the power but should not affect the overall analysis.

For a diary to be considered, at least 7/14 days need to be filled in. Furthermore, best-case, and worst-case scenario will be simulated for the primary outcome implementing lowest and highest values for missing data (see sensitivity analysis).

Descriptive analysis

Descriptive statistics will be used to summarise the characteristics of participants in each arm of the trial. This will include baseline values, treatment schedules, compliance and follow-up. We will show number and percentage or mean and standard deviation for categorical and normally distributed continuous variables respectively. For data severely deviating from a normal distribution, we will present median and interquartile ranges. Probability of observed between groups difference will be provided using either Fisher's exact test, Chi2 test, and or Student's t-test.

Primary outcome analysis

We will analyse the primary outcome of crying time (e.i. individual daily measures of mean crying time in minutes) using random-effects multilevel linear regression. Crying time will be entered as the response variable (dependant) and the link function is identity. Therefore, lack of independence for measures from the same participant will be accounted for. To improve statistical power, the following explanatory variables are to be added to improve the modelling of the between-group differences

- baseline crying time (continuous),
- expectations from treatment (ordinal)
- and age of infants at entry (continuous).

To account for missing data, the data can be categorized and treated as nominal.

Results will be reported as between group difference in crying time in minutes with a 95% confidence interval. Statistical inference for significance of effects of the intervention will be calculated using Wald Chi² test.

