Checking assumptions for primary outcome

a) Assumptions for repeated measures random linear mixed effect

The following assumptions for repeated measures random linear mixed effect need to be tested:

- The explanatory variables are related linearly to the response.
- The errors have constant variance.
- The errors are independent.
- The errors are normally distributed.

A graphical representation will plot the residuals against group allocation. This can indicate if the model fits the data appropriately. The residuals will also be plotted in the order of days after treatment to see any indications of visible trend over time. The residuals will be plotted against the fitted values to test whether there is any non-constant error variance. Finally, a histogram with a normal probability plot and Wilk-Shapiro test will be used to test the assumption of normality for crying-time distribution in each group.

If the distribution of crying time is not Gaussian, then it will be categorised, and the distribution of the response variable will be considered as ordinal, and the link function is logit. When the assumptions for distribution of the residuals are not met, transformation is to be used to make the analysis possible.

b) Testing and accounting for trends over time

Three methods are used to investigate trend over time:

- a. Visual and statistical assessment of trend over time is to be made using fractional polynomials in regression analysis separately for each group.
- b. Repeated measures random linear mixed model is to be used to test interactions between group allocation and days of follow-up. This makes it possible to assess that group differences are constant through time. Explanatory variables are group allocation, interaction between group allocation and number of days of follow-up, baseline crying time day before treatment, infant age at entry, treatment expectations. Linearity of response for the explanatory variable is tested as trends over time using mixed regression analysis.
- c. Day to day means in each group will be calculated using Delta-method linear prediction with fixed portion. Furthermore, linear trend over time will be tested in each group by modelling day to day residuals within the model.

Assumptions are to be verified on the linearity of the progression through time. Transformation is to be used if linearity is not met.

Secondary outcomes analysis

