* Adjusted for baseline crying time, infant age and prior expectations for osteopathic care

Table 3 Effects of treatment on other outcomes including undesirable events

| Outcomes | Test group (TTR) | Control group (GTR) | Between group difference* |
|--|---------------------|------------------------|------------------------------|
| | N=xx | N= xx | (CI 95%; P-value) |
| Parenting Confidence Score [0–45]; mean (SD) | | | |
| Perceived changes in symptoms; n(%) | | | |
| Completely recovered | | | |
| Much improved | | | |
| Slightly improved | | | |
| No change | | | |
| Slightly worse | | | |
| Much worse | | | |
| Vastly worse | | | |
| Weight changes over 14 days (kg); mean (SD) | | | |
| Satisfaction with received care; n (%) | | | |
| Very satisfied | | | |
| Fairly satisfied | | | |
| Neither satisfied nor dissatisfied | | | |
| Fairly dissatisfied | | | |
| Very dissatisfied | | | |
| Unexpected reactions; n(%) | | | |
| More distress | | | |
| Crying more | | | |
| More unsettled | | | |
| Vomiting more | | | |
| Increased feeding difficulties | | | |
| Increased difficulties sleeping | | | |
| Other | | | |
| Serious adverse events; n(%) | | | |
| Death | | | |
| Hospitalisation | | | |
| Long lasting morbidity | | | |
| Any | | | |

* P-values measured using likelihood ratio test in linear/logistic regression, Mann-Whitney U test for ordinal outcomes, Chi2 for categorical

Table 4 Number of sessions, advice given, additional treatment and effectiveness of blinding

| | Test group (TTR) N=xx | Control group (GTR) N= xx | Between group difference* |
|--|---------------------------|---------------------------------|------------------------------|
| | Mean (SD) | Mean (SD) | (CI 95%; P-value) |
| Number of sessions; mean (SD) | | | |
| Advices; n(%) | | | |
| Managing the baby's sleep pattern | | | |
| Managing the baby's feeding pattern | | | |
| Mother's diet | | | |
| Handling the baby | | | |
| Managing the baby's environment | | | |
| Parenting behaviour | | | |
| Reassure parent/guardian | | | |
| Other | | | |
| Medication and remedies; n(%) | | | |
| Prescribed medication | | | |
| Anti-gas drops | | | |
| Herbal supplements | | | |
| Probiotics | | | |
| Non-cow or anti-allergenic formula milk | | | |
| Omeprazol | | | |
| Other | | | |
| Additional care; n(%) | | | |
| General practitioner | | | |
| Accident and Emergency | | | |
| Unplanned hospital admission | | | |
| Another osteopath | | | |
| Paediatrician | | | |

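### Neither the time-trend model nor the primary model lists day as a term, so the constancy check is ambiguous and unequally missing diary days can shift the primary difference by a few minutes

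*SAP*

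**What the plan says.** **Trend model** (SAP section 8, Testing and accounting for trends over time, item b). The terms are listed as "Explanatory variables are group allocation, interaction between group allocation and number of days of follow-up, baseline crying time day before treatment", followed by infant age and expectations. The stated purpose is: "This makes it possible to assess that group differences are constant through time".

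**Primary model.** Three places agree, and none includes day:
- section 5, Primary Outcome measure: "Repeated measures random linear mixed effect adjusting for baseline crying time, expectations for treatment outcome and infant's age";
- section 8, Primary outcome analysis, where "the following explanatory variables are to be added to improve the modelling of the between-group differences" introduces the same three covariates;
- the footnote to Table 2 in section 9: "Adjusted for baseline crying time, infant age and prior expectations for osteopathic care".

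The outcome window runs "from day 1 after the treatment to day 13 after the treatment", which gives 13 daily values per infant.

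**Decline and missing days.** The Background in section 1 expects crying to fall: "These infant behaviors are usually self-limiting (subsiding around 12 weeks after birth". Section 5 sets a day to missing if any hour slot is blank. The Missing data part of section 8 keeps a diary if at least 7 of 14 days are filled in, and asserts that gaps in the diary cost power only.

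**The concern.** A check that the group difference is constant over time is a test of whether two slopes differ. If the model has group and a group-by-day product but no day term, the arm coded 0 is held flat and the product coefficient absorbs the full slope of the other arm. A decline common to both arms, which the SAP itself expects, would then be reported as a treatment-by-time interaction.

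The primary model raises a separate point. Without a day term, each infant's contribution is an average over whichever days were recorded. If crying falls over the two weeks, an infant with only the early days looks worse than one with all 13. When one arm loses more late days than the other, this enters the treatment difference. The assertion that missing days only cost power therefore does not hold for the model as listed.

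**Working it through.** **The plan's own figure.** With a 30-min difference, SD 45 and two-sided 5%, n per arm = 2 × (1.96 + 1.28)² × 45²/30² ≈ 47.3, rounded up to 48. The power at 48 is Φ(30/(45 × √(2/48)) − 1.96) = Φ(1.31) = 90.4%. The stated 48 per arm is reproduced. It serves below as the arm size, with 30 min as the yardstick.

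**Inputs from the SAP.** 48 per arm, 13 days, mean 120 min, SD 45, a decline expected but no slope given.

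**Assumed inputs.** The between-infant SD is 40 and the day-to-day residual SD is 60. The 13-day mean then has SD √(40² + 60²/13) = 43.3, close to the planned 45. The common slope ranges from 0 to -8.6 min/day. The steep end is a straight line from the 180-min entry criterion to 120 min at day 7: 60/7 ≈ 8.6.

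**Trend model.** Identical slopes in both arms, so no true interaction; random-intercept fits, 40 simulated trials per slope.

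| Common slope (min/day) | Product term, no day: mean estimate | Rejected | With day main effect: mean estimate | Rejected |
|---|---|---|---|---|
| 0 | -0.06 | 2.5% | -0.05 | 2.5% |
| -1 | -0.89 | 25% | 0.08 | 7.5% |
| -2 | -1.86 | 82.5% | 0.03 | 2.5% |
| -4 | -3.87 | 100% | 0.21 | 5% |
| -8.6 | -8.54 | 100% | 0.21 | 5% |

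Without day, the coefficient reproduces the common slope. With 40 runs, the Monte Carlo SE is √(0.05 × 0.95/40) = 3.4 points at 5% and √(0.825 × 0.175/40) = 6.0 points at 82.5%. A closed form agrees. The squared deviations of days 1 to 13 sum to 182, so one arm's slope has SE 60/√(48 × 182) = 0.64. At -2 min/day the expected rejection is Φ(2/0.64 − 1.96) ≈ 88%.

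With one slope per arm, the contrast of the two slopes gave the same estimates and rejection rates as the model with a day main effect. Each single slope still tests whether that arm declines, not whether the arms differ.

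**Primary model.** Suppose a share *f* of an arm stops after day 7. The mean recorded day is 7 for a full diary and 4 for a truncated one. The mixed model weights infants by w13 = 1/(40² + 60²/13) and w7 = 1/(40² + 60²/7), so an arm's mean day is

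(f × w7 × 4 + (1 − f) × w13 × 7) / (f × w7 + (1 − f) × w13).

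The bias is the slope times the difference in mean day between arms. For 15% against 0%, the mean days are 6.59 and 7.00, so at -4 min/day the bias is -4 × (-0.41) ≈ 1.6 min.

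| Stopping after day 7, one arm against the other | Slope -2 | Slope -4 | Slope -8.6 |
|---|---|---|---|
| Complete diaries | 0 | 0 | 0 |
| 15% against 0% | 0.8 min | 1.6 min | 3.5 min |
| 25% against 5% | 1.1 min | 2.2 min | 4.7 min |
| 50% against 0% | 2.8 min | 5.6 min | 12.1 min |

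The arm that loses late days looks worse. Fitted models on 50 simulated trials per scenario gave shifts (estimate without day minus estimate with day) of 0.0 for complete diaries at -4, 1.8 for 15% against 0% at -4, 5.6 for 50% against 0% at -4, and 12.0 for 50% against 0% at -8.6. With day in the model, and days unequally missing, the estimates were 0.1 to 1.3 min. These lie within about one Monte Carlo SE (1.3 min) of zero.

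**The case against.** **The coding may be right.** The SAP names Stata 15, where a factor-by-continuous interaction gives one slope per arm. That is the same fit as group + day + group × day, and the slope contrast is valid. This stands. A reader might infer that item b must produce a false interaction; the text supports only that it does so under the 0/1 product reading, or if a single slope is tested against zero. The SAP states neither the coding nor the contrast.

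**It is one diagnostic of three.** Item a models the trend separately in each group, item c calculates day-by-day means, and Table 2 lays out an adjusted difference for each day, which a common trend does not distort. No rule alters the primary estimate because of item b. All of this stands and limits the harm. But the only remedy the SAP names for a trend that breaks its assumptions is transformation; nothing brings day into the primary model.

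**Safeguards exist for missing days.** Missing data are compared between groups, quartile replacement gives best and worst cases, and the per-protocol analysis excludes infants whose diary was not completed daily. These could reveal a problem, but they do not remove it from the primary estimate.

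**Readings that go too far.** A reader might infer that the primary result is biased as it stands. That requires both a trend and a difference between arms in which days are missing. A reader might also take the V0.2 entry in the version history, which lists "baseline crying time, infant age, days within trial and expected outcomes" as agreed co-factors, as a contradiction. A version log describes superseded text, so it is not one. Lastly, one might argue that a random intercept alone inflates the interaction test. The SAP does not say intercept only, and it lists independence of errors as an assumption to check, so that criticism has no basis in the text.

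**Conclusion.** The point holds in a limited form. The trend model as listed allows both a valid test and one that mistakes a shared decline for an interaction (82.5% of runs at -2 min/day, 100% at -4 or steeper, nominal 5%), and the SAP does not say which is meant. The primary model lacks a day term, so missing days are not harmless by construction. For a 15 to 20 point imbalance in early stopping, the bias is about 1 to 5 min of the 30-min target, and it is zero with complete diaries or equal patterns. The 50% against 0% case is an extreme.

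The slopes, the variance split and the stopping patterns are assumptions, because the SAP gives none. As the trend model is a diagnostic and the likely bias is small, this is a worthwhile, inexpensive correction rather than a must-fix.

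**What to change.** 1. **Primary model:** add day (1 to 13) as a fixed effect in sections 5 and 8 and in the Table 2 footnote.
2. **Trend model, item b:** state it as group + day + group × day with the existing covariates. Test only group × day, and define it as the difference in slopes between arms.
3. **Missing data:** replace the assertion that gaps cost only power. Say instead that missing days leave the comparison unbiased only if they are missing at random given the model, with day in it.

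The cost is wording and one term in each model. Categorical day uses 12 degrees of freedom (13 − 1) out of up to 2 × 48 × 13 = 1,248 daily records; linear day uses one. With complete diaries the estimated treatment difference does not change. The edit should be made before group identity is revealed.

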This question asks about overall change in the infant's symptoms, from completely recovered to vastly worse. (Completely recovered, much improved, slightly improved, no change, slightly worse, much worse, vastly worse). These levels are coded numerically in an ordinal manner and are to be compared between groups using non-parametrical approaches.

Experience and satisfaction

Experience was measured using a 5-point likert scale from Very good, fairly good, neither good not bad, fairly poor and very poor.

Satisfaction was measured using a 5-point likert scale from Very satisfied, fairly satisfied, neither satisfied nor dissatisfied, fairly dissatisfied and very dissatisfied.

We also asked if the parent thought osteopathic care helped their baby using a yes, no or unsure response.

Unexpected and or Adverse events

We asked parents about additional care they may have administered to their infants and additional health care consultations they sought during the trial period as a proxy indicator of adverse events, and we also asked directly about any changes in symptoms that cause the parent concern. These included more distress, more crying, more unsettled, more vomiting, increased difficulty in feeding, sleeping and anything else (other).

Serious adverse events are reported by parents and managing osteopaths. These are assessed by the trial managing group and coded as for the reason for being a SAE and the estimated likelihood these are related to the treatment.

6. Randomisation

Block randomisation with variable block size of 4 and 6 generated by CastorEDC.

7. Sample size

From data collected during the pilot phase (n=13), we confirmed crying times as expected by Wolke et al. We estimate the average daily crying time over the two-week follow-up period to be of 120 minutes with a SD of 45 minutes. To detect a minimum of 30 minutes additional reduction in crying time between the intervention and control group with 90% power and a two-sided 5% significance level we would need 48 infants in each arm of the trial. If we allow for a 15% drop out we would need to randomise 112 infants, 66 in each arm of the trial. This sample size calculation is conservative because it disregards the fact that there are repeated measures in each infant and that the model will be corrected for the baseline crying time value. Thus, the actual power will be higher.

| Power | MCID (daily reduction in crying time in minutes) | | | |

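### The model meant to check that the group difference is constant over time lists group by day but not day itself, so a fall in crying common to both arms can pass for a changing treatment effect (should-fix)

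*SAP*

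**What the plan says.** In section 8, under the assumption checks for the primary outcome, part b (trends over time) gives three methods. Item b states: "Repeated measures random linear mixed model is to be used to test interactions between group allocation and days of follow-up". Its purpose follows: "This makes it possible to assess that group differences are constant through time". The terms are then listed: "Explanatory variables are group allocation, interaction between group allocation and number of days of follow-up, baseline crying time day before treatment" and, after it, infant age and treatment expectations. Day appears only inside the interaction.

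No other current passage supplies the term. The primary model, as described in section 5, in the primary outcome analysis of section 8 and in the footnote to Table 2, adjusts for baseline crying, expectations and infant age only.

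The background in section 1 describes the expected course: "These infant behaviors are usually self-limiting (subsiding around 12 weeks after birth". The outcome window is set in section 5: "The primary outcome is the between group average difference in crying time from day 1 after the treatment to day 13 after the treatment".

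**The concern.** A test of whether the group difference is constant compares the two arms' slopes. That requires each arm to have its own slope and the test to be of their difference. The listed terms secure this under neither plain reading.

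- **Single product term, group coded 0/1.** The arm coded 0 has no day term and is fitted as a flat line. The coefficient on the product is then the whole slope of the arm coded 1. Since the arms are blind-coded A and B, the arm held flat, and so the sign of the pattern, depends on an arbitrary label.
- **One slope per arm.** Both slopes are fitted, but a joint test of the listed interaction terms asks whether both are zero, not whether they are equal.

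The test goes wrong exactly when crying falls in both arms, which is what a self-limiting condition leads one to expect. At stake is a false report that the treatment effect changes, or even reverses, over follow-up, and with it unwarranted doubt about an average-difference estimate that is sound.

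**Working it through.** **Inputs from the SAP.** Section 7: "We estimate the average daily crying time over the two-week follow-up period to be of 120 minutes with a SD of 45 minutes"; a 30-minute target difference; "with 90% power and a two-sided 5% significance level we would need 48 infants in each arm of the trial". Section 5: days 1 to 13.

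**Assumptions.** The SAP gives neither a slope nor a day-to-day SD within infants. I use common falls of 0.5 to 3 min/day and within-infant daily SDs of 30, 45 and 60 minutes. For scale, 1 min/day is a drop of 12 minutes between day 1 and day 13, against a planning mean of 120.

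**Reproducing the plan's figure.** n per arm = 2 × (45/30)² × (1.960 + 1.282)² = 2 × 2.25 × 10.51 = 47.3, rounded up to 48. This agrees with the SAP and is used only as the n for the check.

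**Closed form, 0/1 product, balanced days, random intercept.** Suppose both arms fall by s min/day and treatment does nothing.

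- Expected interaction coefficient = −s, the slope of the arm coded 1. It should be 0.
- Sum of squares of day about its mean of 7 = 182.
- SE = SD within / √(48 × 182) = SD within / 93.47, which gives 0.321, 0.481 and 0.642 for SDs of 30, 45 and 60.
- False rejection = Φ(s/SE − 1.96) + Φ(−s/SE − 1.96). Example: s = 1 and SD 45 give s/SE = 2.08 and a rejection rate of 55%.
- Implied false difference (arm coded 1 minus arm coded 0) = −s × (day − 7), so +6s on day 1 and −6s on day 13.

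| Common fall (min/day) | SD 30 | SD 45 | SD 60 | False difference, day 1 to day 13 |
|---|---|---|---|---|
| 0.5 | 34% | 18% | 12% | +3 to −3 min |
| 1 | 88% | 55% | 34% | +6 to −6 min |
| 2 | 100% | 99% | 88% | +12 to −12 min |
| 3 | 100% | 100% | 100% | +18 to −18 min |

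**Simulation.** 200 trials per setting, 48 per arm, SD of the infant average held at 45, REML random-intercept fits, other covariates left out, no treatment effect. Within-infant SD is 45 in these rows.

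| Common fall | Product only: mean coefficient | Product only: rejects | One slope per arm, joint test: rejects | Day added, or contrast of slopes: rejects |
|---|---|---|---|---|
| 0 | 0.06 | 4.5% | 5% | 7% |
| 1 min/day | −0.98 | 51% | 76% | 6.5% |
| 3 min/day | −2.96 | 100% | 100% | 5.5% |

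At 3 min/day and within-infant SD 60, the product model and the joint test each reject in 100% of runs, and the model with day in 3%. With day included, the mean interaction estimate lies between −0.01 and 0.13 min/day in all four settings.

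**Effect on the average.** At the mean day, 7, the false difference is −s × (7 − 7) = 0. The error tilts the difference around the middle of follow-up and leaves the day 1 to 13 average alone when diary days are balanced.

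**The case against.** Item b is an assumption check, not the primary analysis, and the SAP gives no rule by which its result alters the primary model. The omission may be one of wording. If the software fits one slope per arm, neither arm is forced flat, the A/B label is irrelevant, and the fit is identical to group + day + group by day. A contrast of the two slopes is then valid, and the stated purpose points to that contrast. Item a fits trends separately in each group, item c tests trend in each group, and residuals are plotted by day, so parallel falls would probably be seen. All of this stands, and it limits the severity. It does not repair the item: the plan names neither the contrast nor the day term, and items a and c do not correct the test in item b. The V0.2 entry in the version history mentions days within the trial as a co-factor, but that is a change log and does not put the term in the current list.

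A reader might infer more than the document supports:

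- **That the primary result is biased.** It is not, with balanced diary days.
- **That no coding of the listed terms can give a valid test.** The slope contrast does.
- **That Table 2 and Figure 2 will show one arm as a flat line.** The SAP does not say that item c's day-to-day means come from item b's model.
- **That a false finding is near certain.** That depends on a slope the SAP does not give. At 0.5 min/day the rate is 12% to 34%.

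**Conclusion.** The point holds as a should-fix. As listed, the item b model does not deliver its stated purpose when crying falls in both arms. Under the 0/1 product coding, false rejection of a constant difference is about 34% to 88% at a common fall of 1 min/day and 88% to 100% at 2 min/day, against about 5% with day in the model. Under one slope per arm, the joint test of the listed terms fails in the same way (76% at 1 min/day, SD 45), while an explicit contrast of the slopes is sound.

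The direction of the error follows from the model alone. Its size rests on 48 infants per arm with complete days 1 to 13, a linear common fall, a random-intercept structure and an assumed within-infant SD. With no common fall the test behaves properly.

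**What to change.** In item b, list group, day of follow-up, group by day, baseline crying, infant age and expectations, with day in the same form (linear or categorical) as in the interaction. Define the constancy test as the test of group by day with the day term in the model; with linear day this is the contrast of the two arm slopes. State that any day-specific means in item c taken from this model include the day term.

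The cost is one term in the .do file and a sentence or two in the SAP. No new data are needed, and the primary analysis is unchanged.
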